All patients with an identified SzNET in rs-fMRI#1 will be included in the intervention group. Within one and six days after the first scan, the care team will decide and start the intervention with two ASM agents from the list. The intervention phase occurs between rs-fMRI#1 and the day of follow-up rs-fMRI#2 and repeated EEG. The intervention is considered complete and the follow-up tests can be done if the patient received the study ASM for at least 72 hours after the loading dose start, and the second scan must be done within 72 hours of the last intervention ASM dose. The treatment protocol can continue up to a maximum of ten days to improve the opportunity to schedule the scan. Thus, the rs-fMRI #2 must be done at a time between 73h and 312h (the fourth and thirteenth days) after the intervention phase starts, and the subject can still be receiving the intervention at that time.

Once the rs-fMRI #2 is obtained, the subject's ASM treatment can be continued or changed for clinical reasons depending entirely on the care team's decision, then it will not be considered part of the study's intervention phase or be related to the research team.

The intervention aims to validate the epileptogenic background of the SzNET by using an ASM that is known to be effective. We expect the intervention will influence the improvement of the SzNET. We hypothesize that the intervention will selectively modulate the networks caused by epileptogenic activity, while having less to no impact on abnormal networks caused by other phenomena.

The length of the intervention is designed to be adequate for pharmacological modulation of epileptogenic activity. The six-day time frame between the minimum and the maximum treatment protocol time facilitates a window for the rs-fMRI schedule that is a realistic schedule time frame in the ICU.

From the different ASM options the key intervention and first option to be considered as intervention will be phenobarbital + levetiracetam. This specific ASM combination will be communicated clearly to the ICU care teams as the first line of the study intervention. However, for clinical reasons the care team will be free to select any combination of two or more study listed ASM regimens. On day two of maintenance dosing, the phenobarbital serum level will be measured if it is one of the selected medications, and a new loading dose will be given to aim for a level of 40mcg/ml.

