5.2.2. Exclusion Criteria

Any individual who meets one or more of the following criteria will be excluded from participation:

- Previous medical history of Epilepsy by medical chart review.
- Previous medical history of neurological conditions that lead to dependence on care for basic daily activities, by BIS less than 80, examined with the patient's LAR at the time of the in person interview for obtaining the informed consent. If there is medical history of neurological conditions with concerning for impaired independence and the functional status of the patient cannot be addressed properly the patient will be excluded from participation.
- Known allergy/Hypersensitivity or medical contraindications (like porphyria or cardiac arrhythmias) to the treatment protocol options, leaving no potential combination of drugs for the intervention without concerns for adverse events related to known preexistent conditions.
- Considered with Brain death by the care team in the medical record, at any time.
- Is following Commands in 3 different exams from at least 2 different providers.
- Contraindications for MRI scan.
- Prisoner human subjects by medical chart review.
- Confirmed currently pregnant by medical history or by positive blood or urine pregnancy test done in the present hospital admission.
- Treating physician determines the patient is no candidate to receive 2 of the 5 protocol-specified ASM.

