5.7. Blinding

The Follow-up EEG will be assessed by an epileptologist blinded to rs-fMRI#2 results. Those results will not be posted in the medical records or commented with personnel outside the clinical rs-fMRI service until the follow up EEG and its comparison results should be collected. This blinding doesn't need to be removed to reassure the patient SOC.

6. Treatment Design: Procedures

Description For this uncontrolled, open-label, interventional trial, the intervention will be assigned to all enrolled patients with SzNET+ by the first rs-fMRI. The intervention and its compliance criteria are defined as receiving treatment for three to ten complete days with at least two of the following ASM regimens, simultaneously:

1. Phenobarbital 20 mg/kg intravenous loading dose
2. Levetiracetam 60mg/kg intravenous loading dose
3. Lacosamide 200 mg intravenous loading dose
4. Valproate 30 mg/kg intravenous loading dose
5. Fosphenyton 20 mg/kg intravenous loading dose

All the maintenance dose regimens will start the next day to loading dose, and dosing will be calculated for weight and age of both medications within the combination group, until the repeat rs-fMRI. As soon as possible, the research team will inform the care team that the patient has been allocated to the intervention branch so they can decide on two ASM regimens from the previous list to start the treatment. On the same day, the research team will confirm by medical charts the two ASM selected and the date and the time of the first loading dose infusions. The intervention phase takes the time between rs-fMRI#1 and follow-up rs-fMRI and EEG. The rs-fMRI#2 must be performed after at least three complete days of treatment and no later than eleven days after the beginning of the intervention phase, but in case of ASM withdrawal, the rs-fMRI#2 must be done no later than 72 hours from the last dose. As outcome measures are based on data collected the day of the second rs-fMRI, after that day, the care team will be free to adjust ASM according to what better fits the patient without compromising the protocol.

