 - ◆ Rs-fMRI does not require contrast agents to be administered.
 - ◆ In case of tattoos with suspected high levels of ferromagnetic compounds cold compresses can be applied to prevent heating.
 - ◆ Transportation through the hospital to perform the MRI scan can be associated with mechanical risks and support devices malfunction. Trained personnel is in charge of the process, which is supervised by a physician.

○ SzNET Stratification of rs-fMRI

- SzNET (-): with EEG (+) or EEG (-).
 - ◆ N=32
 - ◆ No protocol Intervention-driven, combined ASM is administered.
 - ◆ They will not receive the second fMRI.
 - ◆ They will only be followed at the 3 months post discharge visit if they are scheduled to one of the NSICU Post-Discharge clinics.
 - ◆ MRI scan transportation related AE Review.
- SzNET(+): with EEG(+).
 - ◆ N=11
 - ◆ Proceed with combined ASM Intervention.
 - ◆ Intervention **must** start within 1 to 6 days after enrollment.
 - ◆ AE Review.
- SzNET(+):with EEG(-)
 - ◆ N=11
 - ◆ Proceed with combined ASM Intervention.
 - ◆ Intervention **must** start within 1 to 6 days after enrollment.
 - ◆ AE Review.

○ Study team will inform the family of the rs-fMRI results and upload the official report to EPIC.

Intervention start (Days 1-6 from Enrollment)

- **Clinical Care Team** will choose the intervention regimen.
 - If participant was already on **two** of the protocol-approved ASM, the participant will be required to start the intervention by administering the protocol-driven loading dose infusions outlined for

each of the combined ASMs, or by administering the loading dose for any of the other 5 listed ASM options. A third option in this case is to administer protocol-driven loading dose of one of the current medications and add another of the 5 ASM loading dose and maintenance regimen.

- If participant was already on **one** of the protocol-approved ASM, the participant will be required to start the intervention by administering the protocol-driven loading dose outlined for the ASM that the participant was previously receiving *along with* another protocol-driven ASM loading dose from the ones listed on the protocol.
- If participant **was not receiving any** of the protocol approved ASM, the participant will be administered a loading dose of two of the 5 protocol approved ASM.
- If the clinical care team does not want to use a combination of two of the 5 protocol-approved ASMs, they will not be enrolled into the study.

- **Research Team** will

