7.3. Enrollment

Once informed consent is obtained and the patient is enrolled, the coordinator will double-check previous history of porphyria, allergies, and hypersensitivity to the potential ASM listed in the study to provide a list of the treatment protocols that could be used for the patient if allocated to intervention. On the same day, the study coordinator will schedule the rs-fMRI for the following days and inform the research and the care teams of the scheduled date. This date should be within three days at maximum, and the intervention allocation must be done within six days from enrollment. Considering those dates, the minimum and maximum times from MSABI to the first rs-fMRI are 4, and 48 days correspondingly. The minimum and maximum times from MSABI to the intervention are 5 and 51 days, correspondingly. The family will be told that all the rs-fMRI results will be provided and explained after the follow-up research tests, and no further instructions are needed.

Screening/enrollment interview Activities (Day 0)

- BIS assessment for score (>80) through interview with potential LAR.
- Written Informed Consent Obtained from LAR.

- Consent must be obtained within 90 days from the participant's MSABI.
- Confirming baseline variables are collected through medical chart review.
 - Supratentorial decompressive craniectomy, current GCS score, presence of spontaneous ventilation.
- Verify with the LAR about: porphyria, co-morbidities, medical implants or contraindications for MRI, allergies, and hypersensitivity to the potential ASM.
- Provide a list of the treatment ASMs recommended for this participant that could be used if allocated to intervention.
- Notify Clinical Team about participant enrollment.
 - Verify with study team about which 2 combined ASMs could be administered in case of allocation to treatment.
 1. Phenobarbital 20 mg/kg loading dose
 2. Levetiracetam 60mg/kg loading dose
 3. Lacosamide 10 mg/kg loading dose
 4. Valproate 30 mg/kg loading dose
 5. Fosphenyton 20 mg/kg loading dose

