7.8. Early Discontinuations

Data to be Collected The care team may adjust the treatment plan of all patients to ensure optimal medical management, including the study intervention. Patients who do not meet the treatment criteria (which requires treatment with two of the ASM regimens specified in the protocol for at least 72h from loading dose) or who are unable to undergo the rs-fMRI#2 after completing the minimum intervention time and within 72 hours of their last dose of the intervention protocol will be considered dropouts. For these patients, only the clinical data available at the time of enrollment and their initial rs-fMRI data will be collected for analysis of aim #2. However, this data cannot be used for other outcomes analysis. Nonetheless, we will still collect information about the reason for dropping out and any reported adverse events.

Subjects missing follow-up after rs-fMRI#2 and repeat EEG are performed will have all the study data already collected except for the data asked at one of the NSICU Post-Discharge clinics for exploratory outcomes.

Criteria for Intervention Discontinuation

- Changes in the medical condition that contraindicate the use of at least two of the medications mentioned in the valid intervention list.
- Developing a medical condition that does not allow the rs-fMRI#2 scan.
- Presenting a grade 4 AE.
- Presenting a grade 2 to 3 AE without adequate measures to solve the event and prevent its study-related recurrence.

Requiring more aggressive ASM treatment because of seizures worsening or the need to change one ASM from the protocol list for another listed ASM is allowed.

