Measure the enrollment during all the months of study enrollment. The primary outcome of interest is the rate of monthly enrolled patients.

Aim 6b

Measure the participants dropout among participants during the study. The primary outcome of interest is the dropout rate among the total number of enrolled participants at the end of the study.

We will calculate the summary statistics of these measurements.

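### Section 6 treats a SzNET+ patient whose care team declines two ASMs as not enrolled, contradicting section 7.8; followed literally, it lowers each SzNET+ proportion and the Aim 6b dropout rate

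*Combined protocol and SAP*

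**What the plan says.** Section 7.3 puts enrollment at the consent interview on day 0: "Once informed consent is obtained and the patient is enrolled", the first rs-fMRI is scheduled. Section 6 then sorts patients by the scan result, and "the intervention will be assigned to all enrolled patients with SzNET+ by the first rs-fMRI". Section 4.1 agrees: "All patients with an identified SzNET in rs-fMRI#1 will be included in the intervention group".

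The next step in section 6, Intervention start, covers days 1 to 6 from enrollment. There the care team picks the regimen, and the list of cases ends with: "If the clinical care team does not want to use a combination of two of the 5 protocol-approved ASMs, they will not be enrolled".

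Section 7.8 covers patients who do not receive two listed regimens for at least 72 hours. It classes them as dropouts, records the reason, and says that "only the clinical data available at the time of enrollment and their initial rs-fMRI data will be collected for analysis of aim #2".

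Two earlier checks concern the same drugs. Section 5.2.2 excludes a patient when "Treating physician determines the patient is no candidate to receive 2 of the 5 protocol-specified ASM". The day 0 list in section 7.3 includes: "Verify with study team about which 2 combined ASMs could be administered in case of allocation to treatment".

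Section 5.1 defines the Aim 2 set by who has been scanned, up to the time the first SzNET+ stratum fills. For Aim 6b, section 8.3 states: "The primary outcome of interest is the dropout rate among the total number of enrolled participants at the end of the study". Section 12.5 lists, among its grounds for suspension, five enrolled and allocated patients who fail to complete the intervention phase and follow-up tests.

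**The concern.** The section 6 sentence cannot be applied as worded to someone enrolled days before. The literal way to obey it is to reclassify that person as never enrolled. The step is reached only after a positive scan, so a SzNET- patient can never be removed by it. Removal would then depend on the Aim 2 outcome itself.

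Three results would be affected. The SzNET+ proportion in each EEG stratum would lose positives and no negatives. The Aim 6b rate would lose the refusals from both its numerator and its denominator. The five-patient count in 12.5 would not see them. Feasibility is a stated purpose of this pilot (section 2.2 and Aim 6), and refusal by the treating team after a positive scan is direct evidence on it.

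**Working it through.** **Inputs.** From section 5.1: 11 SzNET+ patients per stratum, SzNET+ rates of 30% (EEG-) and 67% (EEG+), and 22 treated for 20 completers. The Aim 6b denominator is all enrolled (sections 3.6 and 8.3). No document gives a refusal rate, so refusal counts and rates below are assumptions.

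**Plan's own figures.** 11/0.30 = 36.7, rounded up to 37 EEG-. 11/0.67 = 16.4, rounded up to 17 EEG+. The total is 37 + 17 = 54, as stated. The 32 SzNET- patients in section 6 also agree: 54 - 22 = 32.

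**Aim 2 at planned counts.** Deleting k refused SzNET+ patients from a stratum with x positives among n changes x/n to (x - k)/(n - k). This is lower whenever k > 0 and x < n.

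| k per stratum | EEG- | EEG+ | Difference (points) |
|---|---|---|---|
| 0 | 11/37 = 29.7% | 11/17 = 64.7% | 35.0 |
| 1 | 10/36 = 27.8% | 10/16 = 62.5% | 34.7 |
| 2 | 9/35 = 25.7% | 9/15 = 60.0% | 34.3 |
| 3 | 8/34 = 23.5% | 8/14 = 57.1% | 33.6 |

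**Aim 2 in expectation.** The Aim 2 set closes when the first stratum reaches its quota, so both strata need not be complete in it. A form that does not depend on those counts is p(1 - q)/(1 - pq), where p is the true SzNET+ rate and q the share of SzNET+ patients refused.

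- q = 10%: EEG- 0.27/0.97 = 27.8%; EEG+ 0.603/0.933 = 64.6%; difference 36.8 points, against 37.0 with no refusals.
- q = 20%: EEG- 0.24/0.94 = 25.5%; EEG+ 0.536/0.866 = 61.9%; difference 36.4.
- q = 20% in EEG- only: 67.0 - 25.5 = 41.5 points.
- q = 20% in EEG+ only: 61.9 - 30.0 = 31.9 points.

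Each proportion falls. The difference hardly moves under equal refusal and moves in either direction under unequal refusal.

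**Aim 6b.** With d other dropouts, r refusals and N enrolled, the rate is (d + r)/N if refusals are kept and d/(N - r) if they are deleted. The first exceeds the second whenever r > 0 and d + r < N, because the comparison reduces to r(N - d - r) > 0. Take d = 2, the attrition implied by 22 treated for 20 completers, with refusals assumed to come on top.

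- r = 2 (one per stratum): 4/54 = 7.4% kept; 2/52 = 3.8% deleted.
- r = 4 (two per stratum): 6/54 = 11.1% kept; 2/50 = 4.0% deleted.

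**Section 12.5.** With 2 other non-completers and 3 refusals (assumed), the count is 5 and the criterion is met. With refusals relabelled as not enrolled, it is 2.

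**Under section 7.8.** Refused patients stay in every numerator and denominator above, and none of these shifts occurs.

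**The case against.** The strongest reply is that section 7.8 already gives the right handling and that the section 6 sentence is a misplaced eligibility statement. It is in the future tense, it makes no sense for someone already enrolled, and sections 5.2.2 and 7.3 raise the two-drug question before the scan. No section says that a scan is deleted or that a patient is un-enrolled in retrospect. Much of this stands: a reader might infer that the plan prescribes a biased Aim 2 estimate, and the documents do not support that.

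It does not dispose of the point. The earlier checks ask which drugs the patient is suitable for; the section 6 sentence concerns whether the team wants to use them. The team is told of allocation and chooses the regimen only after a positive scan, so a refusal can first arise then. At that moment the section 6 sentence is the instruction on the page, and staff who follow it would not log a dropout for 7.8 to govern.

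Two further readings go too far. One is that Aim 2 as a whole is biased downward; that holds for each proportion but not for the EEG+ minus EEG- difference, which Aim 2 also estimates and tests. The other is to measure the dropout effect among SzNET+ patients only, as 4/22 = 18.2% against 2/20 = 10.0%. Aim 6b is defined on all enrolled, where the same counts give a gap of under 4 points.

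**Conclusion.** The section 6 sentence is wrong as written. It contradicts section 7.8, and it does not fit sections 4.1 and 5.1 or section 6's own rule that every enrolled SzNET+ patient is assigned the intervention. The bias is conditional on following it literally. In that case the direction is certain for each SzNET+ proportion and for Aim 6b, and refusals go missing from the 12.5 count. The sizes shown are illustrative, about 2 to 5 points per proportion for one or two refusals per stratum, because every refusal and other-dropout count is assumed. The planned-count table also takes both full strata as the Aim 2 set. The contradiction itself needs no assumption, and the passages must be reconciled.

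**What to change.** Move the sentence to section 7.2, where the care team is contacted before consent. Section 7.3 would be the wrong place, since it begins once consent has been obtained.

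In section 6, put in its place: *If the care team declines the two-drug regimen after enrollment, the patient remains enrolled, rs-fMRI#1 is retained in Aim 2, and the patient is recorded as a dropout with cause care-team refusal, counted in Aim 6b (denominator all enrolled) and in the section 12.5 count of non-completers.*

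The cost is a short amendment. It changes record-keeping and not treatment, and it uses the dropout and dropout-cause variables already listed in section 4.3. Replacement of the quota place can follow section 5.1. The one downside is that the reported dropout rate may look less favourable.

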7.1. Table of Events

Procedure	ICU Range days Since MSABI event (-1 to -90) prescreening	Screening/Enrollment interview (Must be stable to transport and scan)	Study baseline (Time frame from enrollment, 1 to 3 days)	Intervention Phase Between rs-fMRI #1 (Time frame from enrollment, 1 to 16 days)	Follow up Studies RANGE study day: Between 3 th to 13 th of the intervention start (Time frame from enrollment, 3 to 19 days)	One of the NSICU Post-Discharge clinics At 3 Months from discharge
Recruitment	Eligibility assessments by medical chart review	X	X			
	Informed consent		X			
	Enrollment and rs-fMRI Schedule		X			
	Allocation			X		
Patient or LAR surveys	BIS Pre-MSABI		X			X
	NDDI-E					X
	PROMIS emot. Dist. - Anxiety – Short form					X
	Liverpool AEP					X
	QOLIE-10-P					X
	MoCA					X
Treatment	Study protocol treatment				X*	
	Standard care treatment	X	X	X	X	X
Physical Exams	Glasgow Coma Scale	X	X	X	X*	
	Neurological exam					X
Safety Monitoring	Review of adverse events reported.				X	X*
Clinical tests	Pregnancy test	X				
	Surface EEG	X				
Research tests	Rs-fMRI			X		X*
	Follow-up EEG					X*
	Phenobarbital serum levels				X*	

*Activities including only SzNET + patients.

7.2. Screening

Patients meeting eligibility criteria will be followed by the research personnel to check with the care team the time when the clinical condition of the patient is stable enough to be transported, and MRI scanned. The communication between the research team and the care team will be telephonic. Once the care team accepts and informs that the patient can be screened, the study personnel will check the compliance with inclusion/exclusion criteria listed, call the Patient's family or LAR to inform them about the study and will ask for verbal informed consent to screen the

patient. If the family agrees, the study personnel will schedule the screening/enrollment interview as soon as possible.

Prescreening Assessments Activities (days -90 to -1): The research team will only perform medical chart review of the patients that have an EEG requested.

- Assessing for an ordered clinical care EEG.
 - 2HELP2B Assessment reviewed from the baseline EEG.
 - Stratification of Pre-Screening EEG Data (retrieved from medical record review).
 - EEG(+): had a **presence** of electrographic seizure, electroclinical seizure or ictal-interictal continuum.
 - EEG(-): was **negative** for electrographic seizure, electroclinical seizure or ictal-interictal continuum.
- Medical chart review: Presumed etiologies of disorder of consciousness, Epilepsy antecedent, other comorbidities list, current spontaneous ventilation, height, weight, BMI, BSA, age, sex, pregnancy condition, supratentorial decompressive craniectomy, GCS score and current neurological responsiveness.
- Contacting care team to ask for clinical stability to MRI scan and authorization to contact the LAR.
 - Contacting the LAR to obtain verbal consent to administer the BIA.

Screening/enrollment interview (Day 0)

The screening will involve the in-person interview time period because the Barthel Index score is an additional test required to determine study eligibility. Thus, screening and enrollment will be performed on the same day, which is essential to reduce drop out during the screening period because the clinical state of these patients varies day by day. This strategy is also designed to reduce the anxiety of the families/LAR. The time frame to schedule the screening/enrollment interview after the phone call is flexible only to the extent that it must still meet the max 90 days enrollment deadline from MSABI. That means the available time to schedule the interview depends on the time since MSABI started, to meet the eligibility criteria. On the day of the telephonically scheduled interview with the LAR, the eligibility criteria by medical chart review will be double checked before the interview. If the patient is still eligible, the meeting will proceed. After presenting the study and its purpose, the study personnel will complete the Barthel Index (see appendix A) with the help of the LAR. If the score does not exclude the patient, the interviewer will explain potential risks and benefits and ask for consent for the study.

